7.1.5 Sensitivity analyses

As a sensitivity analysis, the facial inflammatory lesion count at Week 12 will be analyzed via a generalized linear model with a Poisson or negative binomial distribution, depending on the dispersion. Baseline lesion count will be used as a covariate (or offset variable) and treatment group as a factor.

The primary analysis may be repeated with Baseline defined as the mean of Screening and Visit 101.

7.1.6 Supportive analyses

Corporate Confidential Information

Due to the nature of the primary endpoint, heterogeneity may also be observed due to different assessors and sites, hence as a supportive analysis site and/or assessor may also be included in the primary analysis model as fixed effects to investigate site/assessor impact.

Further, supportive analyses may be performed adding other covariates in the model such as baseline IGA and other baseline characteristics in the model.

Corporate Confidential Information

Corporate Confidential Information

8 Statistical methods for safety and tolerability data

All patients within the Safety analysis set will be included in the safety data analysis.

8.1.1 Variables

Adverse events, vital signs (blood pressure, pulse rate, body temperature), ECG intervals, laboratory measurements, immunogenicity as well as patient demographics, baseline characteristics, and treatment information.

8.1.2 Descriptive analyses

Patient demographics and other baseline characteristics

All data for background and demographic variables will be listed by treatment sequence and patient and summarized by period, treatment group. Baseline background data include but are not limited to absolute neutrophil count and neutrophil count percentage of peripheral white blood cell (WBC) count.

Relevant medical history, current medical conditions, results of laboratory screens, drug tests and any other relevant information will be listed by treatment sequence and patient.

Treatment

Use of concomitant medications and data on administration of study drug will be listed by treatment sequence, and patient.

Vital signs

All vital signs data will be listed by treatment sequence, patient, and visit/time and if ranges are available abnormalities (and relevant orthostatic changes) will be flagged. Summary statistics will be provided by period, treatment group and visit/time.

ECG evaluations

QTcF will be listed by treatment sequence, patient and visit/time, and abnormalities will be flagged. Summary statistics will be provided by period, treatment group and visit/time.

Clinical laboratory evaluations

All laboratory data will be listed by treatment sequence, patient, and visit/time and if normal ranges are available abnormalities will be flagged. Summary statistics will be provided by period, treatment group and visit/time.

Adverse events

All information obtained on adverse events will be displayed by treatment sequence and patient.

Adverse events tabulations will be done separately for the following time windows:

- Period 1:
 - Including all data until before Week 12 visit for all patients. A pooled CJM112 group will be added in the summary for P1.
 - Including all data (including follow-up data) for patients not continuing to Period 2. A pooled CJM112 group will be added in the summary for P1.
- Period 2 plus post-treatment follow-up: Including all data from the Week 12 till EoS. A pooled CJM112 and pooled CJM112 groups will be added in the summary for this period.

The number and percentage of patients with adverse events will be tabulated by body system and preferred term with a breakdown by period and treatment. A patient with multiple adverse events within a body system is only counted once towards the total of this body system and treatment. Separate tables and listings will be presented indicating event severity and study drug relationship.

For the legal requirements of ClinicalTrials.gov and EudraCT, two required tables on <on-treatment/treatment emergent> adverse events which are not serious adverse events with an incidence greater than X% and on <on-treatment/treatment emergent> serious adverse events and SAE suspected to be related to study treatment will be provided by system organ class and preferred term on the safety set population. The value of the cutoff value X will be decided with the team when disclosure tables are prepared.

If for a same patient, several consecutive AEs (irrespective of study treatment causality, seriousness and severity) occurred with the same SOC and PT:

- a single occurrence will be counted if there is ≤ 1 day gap between the end date of the preceding AE and the start date of the consecutive AE
- more than one occurrence will be counted if there is > 1 day gap between the end date of the preceding AE and the start date of the consecutive AE

For occurrence, the presence of at least one SAE / SAE suspected to be related to study treatment / non SAE has to be checked in a block e.g., among AE's in a ≤ 1 day gap block, if at least one SAE is occurring, then one occurrence is calculated for that SAE.

The number of deaths resulting from SAEs suspected to be related to study treatment and SAEs irrespective of study treatment relationship will be provided by SOC and PT.

Immunogenicity

All immunogenicity results will be listed by sequence, patient and visit/time.

Other safety evaluations

Pregnancy test results will be listed by treatment sequence, patient and visit/time.

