For 3 patients ^{Corporate Confidential Information} while the positive ADA response was generally characterized with low titers, it cannot be excluded that the ADA response has had a consequence on the target capture profile or on the PASI reduction time course. For the ADA-positive patient ^{Corporate Confidential Information} the presence of ADAs is unlikely to have affected the PASI reduction time course.

Due to the same mechanism of action and similar class of drugs (fully human monoclonal antibodies of IgG1 type) potential risks identified in the large clinical experience for secukinumab are of relevance for CJM112, as the safety profile of CJM112 still remains preliminary in early stages of development. The most frequently reported adverse drug reactions (ADRs) were upper respiratory tract infections (most frequently nasopharyngitis, rhinitis). Most of the events were, however, mild or moderate in severity.

In addition to the above mentioned events, injection site reactions, elevations in liver enzymes, drops in neutrophil counts and ECG abnormalities have been observed sporadically and very rarely in secukinumab trials. These cases have not yet been observed with CJM112. Nevertheless, these constitute events that may be observed and should be monitored routinely, as with any investigational biologic treatment.

As secukinumab was ineffective in a phase II trial in patients with moderate to severe Crohn's disease, patients with active Crohn's disease will be excluded from this study (see [Hueber et al 2012](#)).

Women of child bearing potential (WOCBD) and sexually active males should be informed that taking the investigational drug may involve unknown risks to the fetus if a subject or their partner were to become pregnant during the study. He/she must agree that in order to participate in the study they will adhere to the highly effective contraception requirement for the duration of the study and for 13 weeks after the last dose. If there is any question that the subject will not strictly comply, he/she should not be entered in the study.

Of note, for the present study population, moderate to severe acne, co-morbidities may be observed more frequently than in the overall population, such as depression and suicidal ideation ([Purvis et al 2006](#), [Halvorsen et al 2011](#)). However, frequency of suicidal ideation,

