11.5 Analysis of secondary variable(s)

11.5.1 Safety

Vital signs

All vital signs data will be listed by treatment group, subject, and visit/time and if ranges are available abnormalities (and relevant orthostatic changes) will be flagged. Summary statistics will be provided by treatment and visit/time.

ECG evaluations

All ECG data will be listed by treatment group, subject and visit/time, abnormalities will be flagged. Summary statistics will be provided by period, treatment and visit/time.

Clinical laboratory evaluations

All laboratory data will be listed by treatment group, subject, and visit/time and if normal ranges are available abnormalities will be flagged. Summary statistics will be provided by period, treatment and visit/time.

Adverse Events (AEs)

All information obtained on AEs will be displayed by treatment group and subject.

The number and percentage of subjects with AEs will be tabulated by body system and preferred term with a breakdown by period and treatment. A subject with multiple AEs within a body system is only counted once towards the total of this body system.

Other safety evaluations

Pregnancy test results will be listed by treatment group, subject and visit/time.

Corporate Confidential Information

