8.1.3 Graphical presentation

Boxplots to visualize trends in longitudinal safety data (vitals, ECG, lab parameter) will be created. Mean and overlaying individual figures will be presented for selected parameters from vital signs, ECG and lab.

Corporate Confidential Information

10 References

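### SAP 8.1.2 lists and flags only QTcF, while Protocol 11.5.1 commits to all ECG data; other ECG findings not reported as adverse events have no planned patient-level listing or flag

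*SAP*

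**What the plan says.** Protocol section 11.5.1, under ECG evaluations, states: "All ECG data will be listed by treatment group, subject and visit/time, abnormalities will be flagged". It continues: "Summary statistics will be provided by period, treatment and visit/time".

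SAP section 8.1.2, under the same sub-heading, states: "QTcF will be listed by treatment sequence, patient and visit/time, and abnormalities will be flagged". It continues: "Summary statistics will be provided by period, treatment group and visit/time". This second sentence names no parameter.

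Two other SAP sections are wider than QTcF. Section 8.1.1 gives the safety variable as "ECG intervals". Section 8.1.3 plans graphics: "Boxplots to visualize trends in longitudinal safety data (vitals, ECG, lab parameter) will be created". It adds mean and individual figures for selected ECG parameters.

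ECG is one of the general safety parameters under the secondary safety objective in both documents (Protocol 2.2, SAP 1.3.2). Protocol 8.5.5 records standard 12-lead ECGs and names the Fridericia correction as the one to use for clinical decisions. Protocol 3.7 says that "drops in neutrophil counts and ECG abnormalities have been observed sporadically and very rarely in secukinumab trials", that such cases had not yet been seen with CJM112, and that they should be monitored routinely.

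**The concern.** SAP section 1.1 describes the SAP as the implementation of the analysis planned in the protocol. For ECGs it carries over the protocol's listing and flagging commitment but replaces the whole ECG record with a single derived parameter. The available text gives no reason for this, and the narrower scope does not match the SAP's own variable list.

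What is at stake is the ability to look across patients and arms for ECG changes other than QT prolongation. A listing with flags is where a reader would see, for example, that several patients on one dose had a new change in another interval, each judged unimportant at its own site. If the SAP is programmed as written, those findings have no planned listing. A reader of the report could also take an ECG listing without flags to mean more than that QTcF was unremarkable.

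**Working it through.** No arithmetic applies. The plan gives no figure for this point, and the point depends on no rate, variance or sample size assumption. The check is a comparison of texts.

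**1. Same output, different scope.** The Protocol 11.5.1 and SAP 8.1.2 sentences describe the same product: a patient-level listing by visit, with abnormalities flagged. The protocol's object is all ECG data and the SAP's is QTcF. The SAP also lists by treatment sequence instead of treatment group, but that is a presentation choice used throughout SAP 8.1.2 and loses no data.

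**2. Only the ECG item was narrowed.** For the three repeated-measurement safety domains, the listing scope is:

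| Domain | Protocol 11.5.1 | SAP 8.1.2 |
|---|---|---|
| Vital signs | all data | all data |
| Laboratory | all data | all data |
| ECG | all data | QTcF |

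So this is not a general trimming of safety listings.

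**3. The SAP has more than one ECG scope.** Section 8.1.1 says intervals, the 8.1.2 listing says QTcF, the 8.1.2 summary statistics name nothing, and 8.1.3 refers to ECG in general. Because the summary sentence directly follows the QTcF sentence, a programmer could read it as QTcF only or as all intervals. The text does not settle which.

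**4. Does the protocol itself justify QTcF alone?** Protocol 8.5.5 says which QT correction to use for clinical decisions. That selects a formula and places no limit on what is reported. Protocol 3.7 refers to ECG abnormalities without restricting them to the QT interval.

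**5. What still captures a finding other than QTcF?**

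- *Adverse events.* Under Protocol 9.1 an abnormal test result is an adverse event if it causes signs or symptoms, is considered clinically significant, or requires therapy. SAP 8.1.2 displays all adverse event information.
- *Heart rate.* Pulse is a vital sign (Protocol 8.5.2, SAP 8.1.1). SAP 8.1.2 lists all vital signs and flags abnormalities where ranges are available. Only the ECG-derived rate lacks a stated listing.
- *Graphics.* The boxplots and selected figures in SAP 8.1.3 are not limited to QTcF. They show distributions and courses of numeric parameters. They do not flag abnormal values and cannot show qualitative findings such as rhythm or conduction.

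**6. What is left.** ECG findings other than QTcF that were asymptomatic, judged not clinically significant and untreated, and so not reported as adverse events, have no patient-level listing or flag in the SAP as written.

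**The case against.** The strongest case on the other side accepts the mismatch in wording but holds that little follows from it. Anything clinically significant, symptomatic or treated reaches the adverse event output. Rate is covered by pulse, and numeric ECG parameters can appear in the boxplots and figures. The ECG risk in Protocol 3.7 is a very rare class observation from another antibody, not yet seen with CJM112, and the monitoring language there is what would apply to any investigational biologic. SAP 1.1 places listing shells in a separate tables, figures and listings document that is not available here and might contain fuller ECG listings. The study is a non-confirmatory proof of concept, and no estimate or decision rule is affected.

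Most of this stands, and it rules out several stronger readings that a reader might infer:

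- *That ECG abnormalities other than QT disappear from the planned output.* They do not: step 5 above shows the routes that remain.
- *That the secondary safety objective goes unanswered.* That objective also covers adverse events, laboratory parameters, physical examination and vital signs, and ECG output remains.
- *That the trial would miss a known CJM112 signal.* Protocol 3.7 reports none.

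The objection does not remove the remaining gap. The adverse event route depends on the investigator's judgement of each patient, whereas a flagged listing allows review across patients. Boxplots do not identify patients or flag values. Listing shells present what the SAP specifies, so a wider shell would not cure a narrower SAP sentence; the two would simply disagree.

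**Conclusion.** The discrepancy is real and should be corrected. SAP 8.1.2 limits the ECG listing and flags to QTcF, contrary to Protocol 11.5.1 and out of line with SAP 8.1.1, and no justification is given.

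Its size is modest. It affects descriptive reporting of one component of the secondary safety endpoint, for about 75 planned patients. It affects only findings other than QTcF that were not reported as adverse events. The number of scheduled ECGs cannot be counted, because the body of the assessment schedule is not in the available text. The primary analysis and its decision criteria are unaffected.

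The conclusion rests on two assumptions. First, the SAP sentence will be programmed as written and not widened in the listing shells. Second, the database holds ECG parameters besides QTcF. The recording of 12-lead ECGs and the SAP's reference to intervals make the second likely, but the documents do not list the ECG fields captured. In particular, whether rhythm, conduction or an overall interpretation is recorded is unknown, so the gap extends to those items only where they are.

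**What to change.** In SAP 8.1.2, under ECG evaluations, make the listing and flagging sentence cover all ECG parameters recorded in the database, as Protocol 11.5.1 does, and keep the SAP's ordering by sequence, patient and visit. In the next sentence, state that the summary statistics cover all recorded ECG intervals, by period, treatment group and visit. This brings 8.1.2 into line with SAP 8.1.1 and Protocol 11.5.1. QTcF remains the QT parameter named in Protocol 8.5.5 for clinical decisions. Check the listing shells against the revised text.

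If the restriction to QTcF was deliberate, the SAP should say so, give the reason as a departure from the protocol, and align 8.1.1 with it. Restoring the full scope is simpler.

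The cost is an edit to two SAP sentences and a longer listing, with some added summary output, from data already collected. There is no added patient burden and no change to any efficacy analysis.

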7.1 Study completion and post-study treatment

Each patient will be required to complete the study and thereafter no further study treatment will be made available to them.

Study completion is defined as when the last patient completes their Study Completion visit, and any repeat assessments associated with this visit have been documented and followed-up appropriately by the Investigator, or in the event of an early study termination decision, the date of that decision.

All patients should have safety follow-up for 12 weeks after the last treatment received, whenever possible. The information collected is kept as source documentation. All SAEs reported must be reported as described in [Section 9.2](#) and the SOM. Documentation of attempts to contact the patient should be recorded in the source documentation.

The investigator must provide follow-up medical care for all patients who are prematurely withdrawn from the study, or must refer them for appropriate ongoing care.

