1.4 Study design and treatment

This is a randomized, placebo controlled, subject and investigator blinded, multi-center, non- confirmatory, parallel group, proof of concept study in patients with moderate to severe inflammatory acne. After an initial screening period (up to 4 weeks), the study is conducted in 2 consecutive treatment periods, each of 12 weeks, to show clinical efficacy (in treatment period 1) and potential sustainability of response (in extension period 2). At the beginning of treatment period 1, patients will be randomized to one of 3 treatment groups for the first 12 weeks only:

1. CJM112 at monthly intervals,
2. CJM112 at monthly intervals,
3. Placebo s.c. at monthly intervals.

At the end of treatment period 1, all patients will be offered to the opportunity to remain in the study for the extension period 2. Patients who enter extension period 2 will receive the following treatments:

- Treatment Period 1, . Extension Period 2,
- Treatment Period 1, Extension Period 2,
- Treatment Period 1, Placebo. Extension Period 2, via re-randomization with a randomization ratio of 1:1.

Therefore, exposure to placebo will be limited to a maximum of 12 weeks (treatment period 1). To keep the blinding at each time point, 3 injections will be given.

Whether patients continue or do not continue into extension period 2, all patients will be followed up for safety and potential sustainability of efficacy, for an additional 13 weeks without any treatment.

Figure 1-1: Study design

2 First interpretable results (FIR)

First interpretable results (FIR) will be provided for this trial.
Corporate Confidential Information

Corporate Confidential Information

Corporate Confidential Information

4 Statistical methods: Analysis sets

For all analysis sets, patients will be analyzed according to the study treatment(s) received. This implies that for patients for whom the actual treatment received does not match the randomized treatment, the treatment actually received will be used for the analysis.

All patients who received at least one dose of any study drug will be included in the safety data analysis “safety population”.

The PK analysis set will include all patients with at least one available valid (i.e., not flagged for exclusion) PK concentration measurement, who received any study drug and experienced no protocol deviations with relevant impact on PK data.

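### AE percentages are crude over windows of about 12 and 25 weeks, the Period 2 window merges dosing with off-drug follow-up, and no specified table counts each CJM112-exposed patient once from first CJM112 dose

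*SAP*

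**What the plan says.** The adverse event part of SAP 8.1.2 fixes the measure: "The number and percentage of patients with adverse events will be tabulated by body system and preferred term with a breakdown by period and treatment". It sets three windows.

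- Period 1, all patients: "Including all data until before Week 12 visit for all patients", with a pooled CJM112 column.
- Period 1, second table: "Including all data (including follow-up data) for patients not continuing to Period 2", also with a pooled CJM112 column.
- "Period 2 plus post-treatment follow-up: Including all data from the Week 12 till EoS", with two pooled CJM112 columns whose dose labels are redacted.

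SAP 1.4 gives the lengths: "the study is conducted in 2 consecutive treatment periods, each of 12 weeks", followed by follow-up "for an additional 13 weeks without any treatment". Protocol 7.1 differs: "All patients should have safety follow-up for 12 weeks after the last treatment received". SAP section 5 lists four Period 2 sequences, two of them placebo followed by CJM112, and limits them to patients who take part in the extension.

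SAP 8.1.2 also promises disclosure tables for serious and non-serious events on the safety set. It does not state their window or treatment columns, and the choice between on-treatment and treatment-emergent is still an unfilled template field.

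**The concern.** Safety and tolerability of CJM112 is a secondary objective. Protocol 1.1 and 3.7 report more infections on CJM112 and a possible rise with multiple dosing. A reader looking for accumulation will therefore set the Period 1 percentages beside the Period 2 percentages.

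Those percentages differ in three ways besides any change in risk. The later window is about twice as long. It joins dosing with washout. Other acne treatment is also allowed in it: topicals in Period 2 (protocol 5.2), and other anti-acne treatment in follow-up if medically justified (protocol 3.1). A higher figure could reflect the longer window alone, and a similar figure could hide a higher on-treatment rate diluted by washout.

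The second issue is the count of exposed patients. Most initially active patients appear in both main tables, so columns cannot be added across tables. Follow-up events in patients who stop after Period 1 appear only in the non-continuer table. For an uncommon event, the number of distinct CJM112-treated patients affected, out of all those ever treated, is not a specified output.

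**Working it through.** **Planning figures.** Protocol 3.2 allocates the first 35 patients 3:1:3, giving 15, 5 and 15, and the next 40 patients 1:2:1, giving 10, 20 and 10. The total is 25 per arm. At the 15% dropout in protocol 11.7, 25 × 0.85 = 21.25, which reproduces the stated 21 or so completers per group.

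**Windows.** Period 1 is about 12 weeks. Week 12 to end of study is 12 + 13 = 25 weeks, or 12 + 12 = 24 under protocol 7.1. The ratio is 2.1 or 2.0.

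**Effect on a crude percentage.** The documents give no expected AE rate, so the 12-week percentage p is assumed. Let f be the follow-up hazard as a fraction of the on-treatment hazard, with the on-treatment hazard the same in both periods. The expected 25-week percentage is 1 − (1 − p)^((12 + 13f)/12).

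| f | p = 10% | p = 20% | p = 40% |
|---|---|---|---|
| 0 | 10.0% | 20.0% | 40.0% |
| 0.25 | 12.5% | 24.7% | 47.8% |
| 0.5 | 15.0% | 29.1% | 54.5% |
| 1 | 19.7% | 37.2% | 65.5% |

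Over 24 weeks with f = 1 the figures are 19.0%, 36.0% and 64.0%.

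**Why the split is needed as well as patient-time.** At p = 20% the weekly hazard is −ln(0.8)/12 = 0.0186, or 1.86 first events per 100 patient-weeks. With f = 1 this rate is the same in both windows. With f = 0, time at risk in the merged window is 0.20/0.0186 = 10.76 weeks on treatment plus 0.80 × 13 = 10.40 weeks in follow-up. The merged rate is then 0.20/(10.76 + 10.40), about 0.95 per 100 patient-weeks, half the true on-treatment rate. A rate over the merged window would replace one distortion with another.

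**Denominators.** These assume that all Week 12 completers enter Period 2 and that each redacted Period 2 pooled group is one dose, continuers plus switchers. The limit is the one-sided 95% upper bound with zero events, 1 − 0.05^(1/N).

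| Group | N | Limit |
|---|---|---|
| Period 1 pooled CJM112 | 25 + 25 = 50 | 5.8% |
| Period 2, one dose | about 21 + 11 = 32 | 8.9% |
| Period 2, both doses | about 64 | 4.6% |
| Ever exposed | 50 + 21 = about 71 | 4.1% |

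About 50 × 0.85 = 42 initially active patients would be in both the Period 1 and the Period 2 tables. If only half of each arm entered Period 2, the ever-exposed number would be about 62 (4.7%) and Period 2 over both doses about 37 (7.8%).

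**The case against.** The strongest reply is that the controlled safety comparison is sound. CJM112 and placebo share the same planned window in Period 1, Period 2 has no placebo arm, and the SAP plans no formal comparison of the two periods. The later table's title discloses that it includes follow-up, and protocol 3.7 gives a reason for following patients that long: to catch late events. This is a non-confirmatory study of about 75 patients with descriptive safety summaries, and every event is listed by sequence and patient, so distinct counts can be recovered by hand. All of this stands, and it limits the point to how the tables can be read.

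A reader might infer that placebo switchers never enter a CJM112 denominator. The text does not support that. With four Period 2 sequences and two added pooled CJM112 groups, the natural reading is that each group joins continuers and switchers on one dose. The redacted labels leave this as an inference. What can be said is that switchers are absent from the Period 1 pooled group.

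A reader might also infer that no output of any kind counts each exposed patient once. That cannot be shown either. The disclosure tables leave their window and columns open, and SAP 1.1 places table shells and derived variables in separate documents that are not available here.

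Finally, 37% is the upper end of a range. If no events arose in follow-up, there would be no inflation. Zero is unlikely, since ordinary background events continue off drug and the 13 weeks were set at about five half-lives (protocol 3.1), so drug is still present early in follow-up. The true value within the range is unknown.

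**Conclusion.** The point holds in limited form. In the visible text, AE percentages come from windows of about 12 and 25 weeks with no patient-time, and the longer window does not separate dosing from washout. Percentages therefore cannot be compared between the main Period 1 table and the later table. At unchanged on-treatment risk, an assumed 20% in Period 1 corresponds to between 20% and 37% in the later window. It would be wrong to say that the later figure must be higher.

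No specified table follows every CJM112-exposed patient once from first CJM112 dose. The gain in precision from adding one is moderate. The zero-event limit is 4.1% at about 71 patients, against 4.6% for both doses in Period 2 and 5.8% for Period 1 pooled, under 25 per arm, 15% dropout and full continuation. The larger benefit is a single count that includes all CJM112 exposure and does not count anyone twice.

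The Period 1 comparison with placebo is not affected, nor is any decision rule. The change is worth making because it is cheap and serves a stated secondary objective.

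**What to change.** Keep the planned tables, and amend SAP 8.1.2 before database lock as follows.

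1. Add one AE table from first CJM112 dose to end of study, counting each exposed patient once, by dose and pooled, with patient-time and exposure-adjusted rates. For placebo switchers the clock starts at their first CJM112 dose.
2. In the Period 2 table, show on-treatment and post-treatment follow-up in separate columns, each with its own patient-time.
3. Add patient-weeks to the Period 1 table.
4. State which sequences each Period 2 pooled group contains, and the window and columns of the disclosure tables.
5. Reconcile the 12-week follow-up in protocol 7.1 with the 13 weeks in protocol 3.1 and 3.3 and SAP 1.4, so that the end of the window is defined.

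The cost is one extra table and one derived exposure variable, built from AE dates and dosing records already collected. The ever-exposed table has no concurrent placebo control and should be labelled descriptive only.
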